5.1.4 CT-011 Infusional monitoring

The potential risks that may be related to the administration of monoclonal antibodies in general, adverse events that were possibly related to CT-011 administration in the Phase 1 study, and a few theoretical risks for CT-011 included infusion-related effects. Infusion related effects have not been observed in the Phase I clinical study with CT-011.

Vital signs (temperature, blood pressure, pulse rate, respiratory rate) and ECG will be closely monitored prior to, during, and after drug infusion to avoid general infusion-related toxicity. In the event that severe allergic or hypersensitivity develop, first-line treatment is epinephrine given intramuscularly (0.2 to maximum 0.5 mL aqueous epinephrine 1:1000). Subsequent management of hypersensitivity reactions should follow the institution's protocol. Other known infusion related effects are milder and typically include chills, fever, throat irritation and nausea, which are treated symptomatically. Patients who develop severe infusion reaction requiring intubation will be taken off study.

5.1.5 CT-011 Dose Adjustments

The phase I study showed that CT-011 was well tolerated with no treatment related toxicity at all dose level⁵⁰. Specifically no hematologic toxicity was seen. No dose adjustments or modifications will be made with CT-011 except If DLT was seen with CT-011 at 3 mg/kg in combination with lenalidomide 5 mg, then CT-011 will be reduced to 1.5 mg/kg with lenalidomide 5 mg, which will be the DLT. If adverse events occur that require holding CT-011, the dose will remain the same once treatment resumes. If CT-011 is held for more than 4 weeks, then patient will be taken off study.

5.2 Lenalidomide (RevlimidTM)

5.2.1 Lenalidomide Administration and Schedule

Lenalidomide will be given orally. Schedule as shown in table 5.1

The first dose level starts at 15 mg days 1-21 of a 28 day cycle.

If a dose is missed or vomited up, the dose will not be made up.

Beginning by day 1 of cycle #2 and on day 1 of every cycle thereafter, while all six conditions below have been met, patients will be evaluated for lenalidomide dose escalation.

For patients that:

- Never had a lenalidomide dose reduction due to a toxicity that was probable or definitely related to lenalidomide.
- Maintained platelet count $\geq 50,000$ at all times in the previous cycle
- Minimum ANC $\geq 1,000$ at all times in the previous cycle
- No clinically significant grade 2 or greater non-hematologic toxicities in the previous cycle
- Not yet reached the maximum daily dose of 25 mg of lenalidomide
- Are willing to undergo dose escalation of lenalidomide.
- Serum Creatinine maintained at ≤ 2 mg/dL as in initial eligibility

Then the patient's dose for lenalidomide will be increased by 5 mg per cycle for days 1-21 of a 28 day cycle. If any of the criteria are not met, then no lenalidomide dose escalations will occur during this cycle.

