4.2 Definition of Dose Limiting Toxicity

For the phase I portion, patients will be monitored for safety by assessing toxicities as graded by the NCI CTCAE v4.0. The maximum tolerated dose (MTD) or dose limiting toxicity (DLT) will be defined as one or more of the following toxicities considered to be at least possibly related to one of the study drugs during Cycle 1:

- Grade 3 or greater non-hematologic toxicity with the exception of Grade 3 nausea, vomiting and diarrhea that responds to supportive therapy.
- Grade 4 thrombocytopenia, or grade 3 thrombocytopenia with bleeding, or any requirement for platelets transfusion

- Grade 4 neutropenia persisting for more than 5 days.
- Grade 3 or greater febrile neutropenia (temperature $\geq 38.5^{\circ}\text{C}$)
- Grade 4 anemia, unexplained by underlying disease

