5.3.1 Table 5.1 Adverse events and Dose Adjustment of drugs

Neutropenia	Grade 3 or greater on day 1 of cycle: delay and monitor CBC weekly; if resolves to \leq grade 2 within 4 weeks, resume lenalidomide with 5mg dose reduction. If grade 3 or greater during a cycle, hold lenalidomide for the remainder of the cycle. Resume with 5mg dose reduction for subsequent cycles. G-CSF or GM-CSF are not to be used to avoid dose reductions but can be used for treatment of febrile neutropenia
Febrile Neutropenia	Hold lenalidomide for the remainder of the cycle. Consider G-CSF administration until there is adequate count recovery $ANC \geq 1000/\mu L$ + absence of fever. If neutropenia resolves \leq grade 2, resume lenalidomide at 5 mg dose reduction for subsequent cycles.
Thrombocytopenia	If grade 3 or greater, hold lenalidomide for the remainder of the cycle and until platelets $\geq 50,000/\mu L$. Then resume lenalidomide at 5 mg dose reduction for subsequent cycles.
Anemia	For grade 3 or greater, hold lenalidomide for the remainder of the cycle and until hemoglobin recovers to \leq grade 2.
Fatigue (asthenia, malaise) Lenalidomide or dexamethasone	For intolerable grade 2 or grade 3-4, hold the protocol therapy thought to be probable or definitely related to the reaction until resolves to \leq grade 1, then resume protocol therapy with dose reduction of implicated protocol therapy by one dose level (5 mg for lenalidomide and/or 50% for dexamethasone).
Rash Lenalidomide	If grade 3 or greater, hold lenalidomide until resolves to \leq grade 2, then resume protocol therapy. In the instance of intolerable recurrent rash, stop implicated drug but may continue on study.
Renal insufficiency	For patients with calculated or measured GFR $<30\text{ml/min}$, lenalidomide should be held until creatinine returns to baseline
Venous Thromboembolism	All protocol should be held until the patient is adequately anti-coagulated. Patients with recurrent thrombosis despite adequate anti-coagulation should be removed from protocol therapy.
Suspected Pregnancy	Protocol therapy should be held until pregnancy is ruled out. Discontinue all protocol therapy if pregnancy is positive
Dyspepsia, gastric or duodenal ulcer, gastritis Grade 1-2 (requiring medical management)	Treat with H2 blockers, sucralfate, or omeprazole. If symptoms persist despite above measures, decrease dexamethasone dose by 1 dose level

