The proportion of responses (partial and complete) will be calculated out of all eligible patients who receive any treatment in that disease group who are included in the phase II assessment. Assuming the number of responses is binomially distributed, 95% binomial confidence intervals will also be calculated for the estimate of the proportion of responses. All adverse events will be summarized by the NCI CTCAE v. 4 criteria, and tabulated across all patients who received any treatment with a focus on severe (grade 3+) adverse events and toxicities (i.e. those deemed at least possibly related to study treatment). In addition, we will summarize the proportion of patients who received dexamethasone after being stable disease but without response after 2 cycles of therapy. We will descriptively summarize how many of these patients were converted to response after the addition of dexamethasone. Since the addition of dexamethasone is part of the overall treatment regimen that is dependent on treatment outcome at a certain time point, we will not make other adjustments to the study design to evaluate these patients separately outside of this descriptive summarization of whether or not they received the dexamethasone. We will evaluate other clinical outcomes such as progression-free survival and overall survival using the methods of Kaplan-Meier, although these analyses will be exploratory and primarily to help describe the cohort itself.

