and the pharmacology of the study drug, would be unlikely related to the use of the study drug or the event could be the effect of a concomitant medication

Probable: The event follows a reasonable temporal sequence from administration of the study drug and the event follows a known response pattern to the study drug AND the event cannot have been reasonably explained by an intercurrent medical condition *or* the event cannot be the effect of a concomitant medication

Definite: The event follows a reasonable temporal sequence from administration of the study drug, the event follows a known response pattern to the study drug and based on the known pharmacology of the study drug, the event is clearly related to the effect of the study drug

Unknown: Based on the evidence available, causality cannot be ascribed

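### After a reduction for a possibly related cytopenia, section 5.2.1 can direct a lenalidomide increase while Table 5.1 carries the reduction forward, and no section says which prevails

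*Combined protocol and SAP*

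**What the plan says.** **Increase rule (section 5.2.1).** From day 1 of Cycle 2, and on day 1 of each later cycle, patients are checked for a lenalidomide increase. One condition concerns earlier reductions: "Never had a lenalidomide dose reduction due to a toxicity that was probable or definitely related to lenalidomide". Six others are listed:

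- a platelet floor and an ANC floor, each to hold "at all times in the previous cycle"
- "No clinically significant grade 2 or greater non-hematologic toxicities in the previous cycle"
- serum creatinine within the entry limit
- current dose below 25 mg
- the patient's willingness

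If all are met, the text directs a 5 mg increase. If any fails, there is no increase in that cycle.

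**Reduction rule (Table 5.1 in section 5.3.1).** For neutropenia of grade 3 or more during a cycle, lenalidomide is held for the rest of the cycle, and then: "Resume with 5mg dose reduction for subsequent cycles". The febrile neutropenia and thrombocytopenia rows carry a 5 mg reduction forward in the same way. None of the three rows asks about attribution or mentions going back up.

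**DLT rule (section 4.2).** A DLT is a listed toxicity "considered to be at least possibly related to one of the study drugs during Cycle 1".

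**Continuing after a DLT (Synopsis, Study Design).** A patient with a haematologic DLT related to lenalidomide may stay on treatment with a lenalidomide reduction if the event resolves, the investigator judges this to be in the patient's interest, and the patient qualifies for the next cycle. The DLT still counts towards the MTD.

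**Attribution (section 10.2).** Possible, probable and definite are separate categories.

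**The concern.** The two dosing rules use different tests. The three cytopenia rows reduce the dose without regard to cause, whereas 5.2.1 disregards any reduction whose cause was rated only possible. The same patient can thus fall under one rule that holds the dose down and another that directs it up, with nothing to settle the matter.

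This bears on safety because the patient may be one whose DLT was counted, and the increase would bring that patient back to the dose at which the DLT occurred, or above it. It bears on the analysis because response after 4 cycles is the phase II decision variable in section 6.1.2. The lenalidomide exposure behind that response could differ between sites that each follow the protocol as written.

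**Working it through.** The plan states no figure on this point, so there is none to reproduce. The check sets the rules side by side and traces the dose.

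**1. Does a possibly related reduction escape the 5.2.1 bar?** Yes. The bar names probable and definite only, and section 10.2 makes possible a separate category.

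**2. Does another section settle the conflict?** No. Section 5.6 starts the next cycle one level lower when lenalidomide was omitted for the rest of the previous cycle, but says nothing about later cycles. Neither 5.2.1 nor 5.3.1 refers to the other on this question.

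**3. Can it follow a counted DLT?** Yes, by one route. Section 4.2 needs only possible attribution, and the Synopsis allows continuation after a haematologic DLT related to lenalidomide. A DLT is not required, however. The neutropenia and thrombocytopenia rows act from grade 3, and neither dosing section is limited to phase I.

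**4. When can the first increase come?** For a Cycle 1 event, not before Cycle 3. Cycle 2 starts at the reduced dose under Table 5.1 and section 5.6, and the Cycle 1 counts would also fail the ANC or platelet condition.

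**5. Dose trace.** Assumptions: a grade 3 or higher neutropenia or thrombocytopenia in Cycle 1, rated possible and resolved in time; a 5 mg reduction; all other 5.2.1 conditions met from Cycle 2 on.

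- Both rules: d1 = starting dose, d2 = d1 − 5.
- Under 5.2.1: d(c) = min(25, d(c−1) + 5) for c ≥ 3.
- Under Table 5.1: d(c) = d2 for c ≥ 3.

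| Start (mg) | Rule | C1 | C2 | C3 | C4 | C5 |
|---|---|---|---|---|---|---|
| 25 | 5.2.1 | 25 | 20 | 25 | 25 | 25 |
| 25 | Table 5.1 | 25 | 20 | 20 | 20 | 20 |
| 15 | 5.2.1 | 15 | 10 | 15 | 20 | 25 |
| 15 | Table 5.1 | 15 | 10 | 10 | 10 | 10 |

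If the event is rated probable or definite, 5.2.1 gives no increase and the two rules agree.

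**6. Scheduled lenalidomide before the 4-cycle assessment.** Cycles 2 to 4 have 21 dosing days each. Cycle 1 is left out because the day on which dosing is held is unknown.

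- Start 15 mg: (10 + 15 + 20) × 21 = 945 mg against (10 + 10 + 10) × 21 = 630 mg; ratio 945/630 = 1.50.
- Start 25 mg: (20 + 25 + 25) × 21 = 1,470 mg against (20 + 20 + 20) × 21 = 1,260 mg; ratio 1,470/1,260 = 1.17.

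The gap in daily dose at Cycle 4 is 20 − 10 = 10 mg for a 15 mg start and 25 − 20 = 5 mg for a 25 mg start. At Cycle 5 the 15 mg start reaches a gap of 25 − 10 = 15 mg.

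**The case against.** The best defence is that 5.2.1 is a deliberate, more specific rule. By excluding only probable and definite causes, it implies that other reduced patients remain eligible for an increase. Table 5.1 would then set the dose on resumption and 5.2.1 would govern what follows. In support, several dexamethasone rows of the same table say outright that the drug is not to be restarted, while the cytopenia rows contain no such words. This reading is possible, but it is stated nowhere. The 5.2.1 condition itself treats a qualifying reduction as a lasting bar, and the cytopenia rows give no route back. If reversal is intended even after a counted DLT, a site cannot be left to infer it.

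A second objection is that different attribution thresholds for different purposes are not an error. That stands. The DLT threshold serves to count events, and the threshold in section 6.1.2 ("those deemed at least possibly related to study treatment") serves to tabulate them; neither governs re-escalation. The point rests on opposite dose instructions, not on unequal thresholds.

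Third, the route through a DLT is narrow. The event must be haematologic, related to lenalidomide yet rated only possible, and resolved, with the investigator in favour of continuing. A DLT may also be attributed to CT-011. This limits how often the most serious case can arise, but does not remove it.

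Fourth, the traced paths are the upper end. They need every condition met in every cycle, and a further cytopenia of grade 3 or more would trigger Table 5.1 again.

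**Conclusion.** The conflict is real and confined to three rows of Table 5.1: neutropenia, febrile neutropenia and thrombocytopenia. For a possibly related Cycle 1 event it begins at Cycle 3. On the assumptions of the trace, a 25 mg patient returns to the event dose, and a 15 mg patient returns to it in Cycle 3 and exceeds it from Cycle 4. The trace also assumes that the reduction after a DLT, which the Synopsis describes as standard of care, is the 5 mg step of Table 5.1, and that an event rated possible can count as lenalidomide-related. How many patients would be affected cannot be derived from the documents.

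Four stronger readings are not supported:

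- *That attribution is the only bar to an increase.* Six other conditions apply, and a patient who started at 25 mg cannot go above that dose.
- *That the fatigue row has the same conflict.* It says "hold the protocol therapy thought to be probable or definitely related to the reaction", which is the standard used in 5.2.1, so the two agree.
- *That the bar misses many events.* No section gives the share of reductions rated possible. Section 10.2 requires for probable "AND the event cannot have been reasonably explained by an intercurrent medical condition" but prints an alternative limb on concomitant medication. Treating the myeloma itself as an intercurrent condition would be the reader's inference.
- *That the MTD is compromised.* DLTs are counted in Cycle 1, before any such increase. The stated error rates of the 29-patient rule are also untouched.

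What remains is a safety-relevant inconsistency that should be corrected. It also leaves exposure by the 4-cycle assessment dependent on which section is followed, both for the 23 phase II patients and, in principle, for the 6 phase I patients pooled with them.

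**What to change.** Reconcile section 5.2.1, the three cytopenia rows of Table 5.1 in section 5.3.1, the Synopsis text on continuing after a DLT, and section 4.2, so that no patient can receive opposite dose instructions. State expressly whether a reduction made under those rows may be reversed and, if so, when, including after a counted DLT. Say which section governs if they still overlap. The choice of clinical rule belongs to the investigators, and none is proposed here.

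While that list is open, correct its count: 5.2.1 announces six conditions and lists seven.

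The cost is a protocol amendment of a few sentences, with no change to sample size or decision rule. Depending on the choice made, fewer patients may be titrated upward.

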4 STUDY DESIGN AND DURATION

4.1 Study Design

This is a non-randomized open-label phase I/II study for patients with relapsed and refractory multiple myeloma. For the phase I part, we will conduct a standard 3+3 design over 4 main dose levels cohorts evaluating 1.5, 3, 3, and 6 mg/kg of CT-011 given intravenously every 4 weeks (every 28 days) on day 3, and lenalidomide given at 15, 15, 25, and 25 mg orally daily on days 1-21 of a 28-day cycle, to determine the maximum tolerated dose. The phase II will commence once the MTD is determined, and this dose level combination for CT-011 and lenalidomide will be used for the phase II portion of this trial. Patients will be assessed for response at the end of cycle 4 or sooner if necessary according to the IMWG response criteria.

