4.3 Dose Escalation/De-escalation

If a DLT occurs in 2 or more patients on a dose level during the first cycle, the MTD will be exceeded and we will consider this dose level to be intolerable. If a DLT occurs in 1 of 3 patients during this time, an additional 3 patients will be enrolled at that dose level cohort and evaluated for DLT before dose escalation can proceed. If no other patient in the cohort has a DLT, escalation to the next cohort may proceed 1 week later from the last included patient on the current cohort. If a second patient in a cohort has a DLT, MTD determination will then be conducted by one of the following schemes:

- If ≥ 2 of 3 patients in cohort 1 exhibit a DLT at the dose of 1.5 mg/kg CT-011 in combination with lenalidomide 15 mg, 3 more patients will be enrolled at a de-escalated dose level cohort. This de-escalation cohort (Cohort -1) will use the same dose of CT-011 (1.5 mg/kg) in combination with 10 mg lenalidomide. If no further DLTs are observed, we will consider dose escalation of the CT-011 with this lower dose of lenalidomide such that the dose escalation of CT-011 to 3 mg/kg with lenalidomide 10 mg will proceed in the next cohort. However, if ≥ 2 patients experience DLT with CT-011 1.5 mg/kg and lenalidomide 10 mg, then we will further de-escalate lenalidomide to 5 mg and enroll 3 more patients on CT-011 1.5 mg/kg combined with lenalidomide 5 mg. The same criteria for MTD will be used for these de-escalation dose level cohorts.
- If ≥ 2 patients in cohort 2 exhibit a DLT at the dose of 3 mg/kg CT-011 in combination with lenalidomide 15 mg, we will explore tolerability of an intermediate dose level of lenalidomide, where 3 patients will be enrolled and treated with 3 mg/kg of CT-011 in combination with 10 mg lenalidomide. The dose escalation of CT-011 to 6 mg/kg with lenalidomide 10 mg will proceed in the next cohort if no more than one DLT is observed in the 3 mg/kg CT-011+10mg lenalidomide cohort.
- If ≥ 2 patients in cohort 3 exhibit a DLT at the dose of 3 mg/kg CT-011 in combination with lenalidomide 25 mg, 3 more patients will be enrolled at the 3 mg dose of CT-011 in combination with 15 mg lenalidomide. If there is < 1 DLT with CT011 3mg/kg and lenalidomide 15 mg, this will be defined as the MTD. If there are 2 or more DLT, then 3 additional patients will be enrolled at the CT-011 3mg/kg and lenalidomide 10 mg, which will become the MTD.

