- If ≥ 2 patients in cohort 4 exhibit a DLT at the dose of 6 mg/kg CT-011 in combination with lenalidomide 25 mg, 3 more patients will be enrolled at the 6 mg dose of CT-011 in combination with 15 mg lenalidomide. If there is < 1 DLT with CT011 6mg/kg and lenalidomide 15 mg, this will be defined as the MTD. If there are 2 or more DLT, then 3 additional patients will be enrolled at the CT-011 6mg/kg and lenalidomide 10 mg, which will become the MTD

To determine dose escalation, we will focus on the number of patients who experience dose limiting toxicity; i.e. a patient who experiences more than one DLT will be counted only once.

Discontinuation of treatment due to disease progression will not constitute a DLT.

In the Phase 1 portion of the study, subjects who withdraw or prematurely discontinue treatment before completing the first treatment cycle for reasons other than toxicity and DLT will be replaced.

After 4 cycles of therapy or earlier if clinically indicated, response determination will be assessed by the IMWG criteria. At the end of Cycle 4, if a subject has responded (complete or partial response) or has stable disease, dosing with CT-011, lenalidomide and dexamethasone(if initiated after cycle 1-2) will continue for a minimum of 8 additional cycles or until withdrawal.

For the Phase II portion

Upon determination of the MTD in the phase I portion of this trial, the phase II portion of the study will commence enrollment at the MTD determined in the phase I portion with CT-011 in combination with lenalidomide. In the event that a MTD is not established, safety and tolerability data collected in the Phase I portion of the study will guide decisions on dosing of CT-011 in the phase II trial.

Dexamethasone 40 mg orally weekly may be added if only stable disease after 3 cycles according to the IMWG criteria (section13). Dexamethasone can be reduced to 20 mg based on tolerability or if patient is 70 years or older.

During the phase II portion of this trial, we will not evaluate patients for DLTs as was done in the phase I portion; however, we will use the DLT criteria to identify potential toxicity and tolerability concerns occurring at any cycle to initiate further evaluation to ensure safety of patients. An independent Data and Safety Monitoring Committee will continue oversight of this trial. See Appendix E for details.

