5.1 CT-011

5.1.1 Schedule

Table 5-1: Treatment Regimen During Phase I Study: 28 day Cycle

	CT-011- mg/kg day 3
Cohort -1	1.5
Cohort -2	1.5
Cohort 1	1.5
Cohort 2	3
Cohort 3	3
Cohort 4	6

	Lenalidomide- mg Days 1-21
Cohort -1	10
Cohort -2	5
Cohort 1	15
Cohort 2	15
Cohort 3	25
Cohort 4	25

CT-011 is an investigational agent supplied by Medivation, Inc., It is supplied for this protocol for clinical trial use only and it is not commercially available.

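### Section 5.2.1 raises lenalidomide to a fixed 25 mg without reference to the MTD, so on its face it takes qualifying patients above any MTD that carries less than 25 mg

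*Combined protocol and SAP*

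**What the plan says.** Section 5.2.1 sets the titration rule. It applies "Beginning by day 1 of cycle #2 and on day 1 of every cycle thereafter". If the listed criteria are met, the patient's "dose for lenalidomide will be increased by 5 mg per cycle for days 1-21 of a 28 day cycle". The criteria cover earlier lenalidomide reductions, platelets, ANC, non-hematologic toxicity, creatinine, the patient's willingness, and one dose limit: "Not yet reached the maximum daily dose of 25 mg of lenalidomide". (The lead-in counts six criteria; seven are listed.) None mentions the MTD, the assigned cohort or the phase.

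For phase II, Section 4.1 says of the MTD that "this dose level combination for CT-011 and lenalidomide will be used for the phase II portion of this trial". Section 4.3 says that phase II "will commence enrollment at the MTD determined in the phase I portion with CT-011 in combination with lenalidomide". Section 4.5 has 23 further subjects treated at the MTD.

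On tolerability, Section 4.3 states: "If a DLT occurs in 2 or more patients on a dose level during the first cycle, the MTD will be exceeded". It then mostly de-escalates by lowering lenalidomide while keeping the CT-011 dose. In the cohort 2 branch, for example, an intermediate level is opened, "where 3 patients will be enrolled and treated with 3 mg/kg of CT-011 in combination with 10 mg lenalidomide". An MTD with 15, 10 or 5 mg of lenalidomide is therefore a planned outcome. Section 5.1.5 keeps CT-011 essentially fixed within a patient.

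**The concern.** When a level fails, the plan lowers lenalidomide and leaves CT-011 where it was. Titration under 5.2.1 then raises lenalidomide again, 5 mg at a time, at that same CT-011 dose. The steps lead back towards the combination that failed, and nothing in 5.2.1 stops them at the MTD.

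Two things are at stake. The first is safety: patients could be moved, by instruction and before their cycle 4 assessment, to a combination that phase I called intolerable or never tested. The second is interpretation: the 4-cycle response rate that drives the decision rule in Section 6.1.2 would describe a titration above the MTD, while Section 4.1 says that the MTD combination is what phase II uses. The six phase I patients at the MTD who count towards the 29 fall under the same rule.

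**Working it through.** **The plan's own figures.** The plan gives no figure for titration. The phase II error rates in Section 6.1.2 reproduce by exact binomial (n = 29, response rates 0.25 and 0.50, cut-offs 9 and 12): alpha 0.039, beta 0.031, eta 0.834, pi 0.868, against the stated 4%, 3%, 0.83 and 0.87. They do not depend on this point.

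**Does 5.2.1 reach phase II?** This is an inference. It is the only lenalidomide administration section, it names no phase, and the single schedule of events (5.8.6, footnote f) provides for a blood count in cycles with an escalated dose. Against that, it refers to a table headed "Table 5-1: Treatment Regimen During Phase I Study: 28 day Cycle".

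**Branches.** Inputs: the de-escalation rules in 4.3, +5 mg per cycle from cycle 2, ceiling 25 mg, CT-011 fixed. Doses are CT-011 mg/kg / lenalidomide mg.

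| Rejected in phase I | MTD | Where titration leads |
|---|---|---|
| 1.5/15 and 1.5/10 | 1.5/5 | 1.5/10 in cycle 2: rejected |
| 1.5/15 and 3/10 | 1.5/10 | 1.5/15 in cycle 2: rejected |
| 1.5/15 | 3/10 | 3/15 in cycle 2: untested, more CT-011 than the rejected level |
| 3/15 and 6/10 | 3/10 | 3/15 in cycle 2: rejected |
| 3/15 | 6/10 | 6/15 in cycle 2: untested, more CT-011 than the rejected level |
| 3/15 and 3/10 | 1.5/15 (assumed; 4.3 is silent) | 1.5/20, then 1.5/25 in cycle 3: untested |
| 3/25 | 3/15 | 3/25 in cycle 3: rejected |
| 3/25 and 3/15 | 3/10 | 3/15 in cycle 2: rejected |
| 6/25 | 6/15 | 6/25 in cycle 3: rejected |
| 6/25 and 6/15 | 6/10 | 6/15 in cycle 2: rejected |

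Seven of the ten branches return to exactly a rejected combination by cycle 2 or 3. The other three go above the MTD to an untested one.

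**Exposure before the cycle 4 assessment**, for a patient who qualifies every cycle (21 dosing days per cycle, 4 × 21 = 84):
- MTD at 15 mg: 15, 20, 25, 25 mg. Mean (15 + 20 + 25 + 25)/4 = 21.25 mg, which is 21.25/15 = 1.42 times the MTD dose. Days at 25 mg: 2 × 21 = 42 of 84.
- MTD at 10 mg: 10, 15, 20, 25 mg. Mean 70/4 = 17.5 mg, 1.75 times the MTD dose. Days at 15 mg or more: 3 × 21 = 63 of 84.

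**How often.** The plan gives neither a DLT rate for the combination nor a qualifying rate, so both are assumed. Under the 3+3 rule, a level with DLT rate p clears with probability c(p) = (1−p)³ + 3p(1−p)⁵, which is 0.906, 0.709, 0.494 and 0.309 at p = 10, 20, 30 and 40%. Once opened, cohort 3 rejects 3/25 with probability 1 − c(p) = 0.09, 0.29, 0.51 and 0.69. If the MTD is below 25 mg and 25, 50 or 75% of the 23 new phase II patients qualify often enough to be titrated that far, 5.8, 11.5 or 17.3 of them (about 6, 12 or 17) are affected.

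**Phase I timing.** Let the last cohort 2 patient (3/15) start on day 0. If this patient qualifies and has no delay, cycle 3 starts on day 56 at 3/25. If the one-week break follows the 28-day DLT evaluation, cohort 3 opens no earlier than day 28 + 7 = 35 and completes cycle 1 on day 35 + 28 = 63, after the dose rise. If the week runs inside the 28 days, cohort 3 completes cycle 1 on day 28 + 28 = 56, the same day. Cohort 2 patients who started earlier reach 3/25 sooner.

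**The case against.** The best defence is that 5.2.1 was written for phase I. It refers to a phase I table and says that the first dose level starts at 15 mg, which is cohort 1. A site could take Sections 4.1 and 4.5 as fixing the phase II dose. That reading is available, but no text suspends 5.2.1 in phase II. One can also reconcile the sections by saying that patients only start at the MTD, but that reading confirms dosing above it.

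The safeguards are real. Titration is for willing patients who tolerated the previous cycle, so their DLT risk is probably below the phase I rate. Biweekly counts in cycles 1 to 4, a day-17 count after escalation, the hold-and-reduce table in 5.3.1, DLT criteria applied at any cycle, and DSMC review can all limit harm and may halt escalation for later patients. This stands. But the individual criteria look back at the lower dose, and the rest act once the higher dose has begun.

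It is also fair that 25 mg is the lenalidomide dose of the two phase III trials in Section 1.3.1, and that CT-011 alone reached 6 mg/kg without an MTD (Section 1.4.2). Nothing in the documents shows that high DLT rates for the combination are likely. That bears on how often the problem arises. It does not answer a phase I result that rejects the combination.

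Finally, titration is a written part of treatment, so the response rate remains a valid estimate for the titrated regimen. However, Section 6.1.2 explains how response-dependent dexamethasone is handled and says nothing on titration, while Section 4.1 names the MTD combination.

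**Conclusion.** The conflict is in the text and depends on no assumed rate: when the MTD carries less than 25 mg, 5.2.1 and the statements that phase II is treated at the MTD cannot both be followed for a qualifying patient. The size, for a patient qualifying every cycle, is a mean dose 42% above an MTD of 15 mg, or 75% above one of 10 mg, over the four cycles before response is assessed. How many patients this affects is unknown; the ranges above rest on assumed rates.

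Several stronger readings are not supported:
- A reader might infer that phase II patients will be escalated into a rejected combination. That requires an MTD below 25 mg, 5.2.1 applying in phase II, and a patient who qualifies. On three of ten branches the combination is untested, not rejected.
- A reader might take the chance that cohort 3 or cohort 4 fails as the chance of an MTD below 25 mg. Under the rule in the synopsis that the MTD is the level just below the failed one, a failed cohort 4 leaves 3/25 as the MTD.
- A reader might conclude that cohort 2 patients always reach 3/25 before cohort 3 is cleared. For the last cohort 2 patient, one reading of the one-week rule gives the same day.
- MTD determination is not compromised, because DLTs are counted in cycle 1, before titration. The n = 29 design is unaffected.

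**What to change.** In Section 5.2.1, replace the fixed ceiling with:
- in phase II, the lenalidomide dose of the MTD combination;
- in phase I, or if no MTD is established, the highest lenalidomide dose already cleared at the same or a higher CT-011 dose;
- in no case more than 25 mg.

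State in the same place that the rule applies in both phases, and correct the count of criteria from six to seven.

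The drafting cost is small. The clinical cost should be stated openly: phase II patients start at the MTD, so this ends up-titration above it, even for those who tolerate lenalidomide well. In phase I it delays increases until the relevant level is cleared. The sample size, decision rule and error rates stay as they are. If the sponsor does want phase II titration above the MTD, the plan should say so, justify it against the phase I result, and describe the response rate as that of a titrated regimen.
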